patients to exhibit mild frailty (RAI 16-25) with essentially intact independence and capacity for prehabilitation. Higher degrees of frailty may impose barriers to full participation, but characterizing those limitations is an important component of this pilot. We will stratify enrollment to ensure approximately equal enrollment of cardiac and non-cardiac thoracic patients.

**C.3. Prehabilitation procedures.** Prehabilitation will last 3-6 weeks—a time frame that does not delay surgery, corresponds to the typical lag for surgical scheduling, and strikes a pragmatic balance between improving physiologic reserve without unduly delaying definitive surgical therapy. Although the training intervention is only 3-6 weeks, studies repeatedly demonstrate neuromuscular strengthening, diminished inflammation, and respiratory improvements within this time. Further, the program also fosters continuity between preoperative training and traditional postoperative rehabilitation, facilitating rapid mobilization and progressive exercise after surgery. Strategies like this enhance functional recovery and reduce the risks of subsequent episodes of disability (e.g., readmission or loss of independence). If clinical contexts such as neoadjuvant chemotherapy or worsening angina require shorter (or permit longer) durations of training, we will examine these events in order to inform the optimal duration of prehabilitation for a larger clinical trial.

**(a) Safety.** Prehabilitation will begin in a telemetry-monitored, hospital-based setting to train patients in the home-based exercises and establish safe targets of exertion. If and as safety is established, exercise will shift to the home with weekly telephone/ VA Video Connect contact to ensure safety and reinforce technique. Remote telephone and VA Video Connect monitoring will be enhanced by the relationships, familiarity, and trust established during the hospital-based sessions. Although safety concerns will require some patients to complete all exercise in monitored, hospital-based settings, we anticipate that many patients will safely transition to home-based exercise after 1-4 hospital-based sessions. Study staff will initiate withdrawal procedures for patients who demonstrate insufficient cognitive or physical capacity to safely carry out the prescribed activities.

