**(b) Hospital-based training.** Twice weekly 1-hour hospital sessions will be closely monitored and continue until participants demonstrate: (a) mastery of prehabilitation techniques; and (b) compliance with safe targets of exertion that do not induce cardiac symptoms. All patients will complete at least 1 sessions with telemetry to rule-out significant arrhythmia, but they will continue as long as needed to ensure that exercise can safely shift to the home. *Aerobic training* will focus on seated pedaling. Leg pedaling is preferred, but in cases of lower extremity disability, upper extremity exercise will be implemented. After a 3-5 minute warm-up at a low intensity of an 7-9 on the Borg Rating of Perceived Exertion (RPE) scale, patients will be coached to reach 30 minutes of continuous (through bouts of 10 minutes or more to work up to the 30minutes), moderate exertion (RPE 11-13). If this exertion induces cardiac symptoms, the target will be adjusted down until a safe level is established. *Strength training* will use body weight and resistance bands (TheraBand™) at RPE 11-13 to focus on a spectrum of antagonist muscles to support the core abdominal and thoracic muscles impacted by surgery. *Coordination training* will involve exercises designed to strengthen the proper form of transitional movements required after surgery such as lying-to-side-lying, side lying-to-sitting, seated scooting, and sitting-to-standing. *Respiratory muscle training (RMT)* requires that subjects inspire and exhale through a mouthpiece at a comfortable rate using diaphragmatic breathing techniques while wearing a nose clip. The RMT device prohibits subjects from inhaling or exhaling until specific negative or positive pressures are achieved. Thresholds devices will be used and set at 40% of each patient's maximal inspiratory pressure (MIP) performed on the Pro2 device. Training will involve 5-20 breaths depending on patients capacity on the threshold device with resistance increased weekly based on RPE with a goal of moderate exertion (RPE 11-12) on both inhalation and exhalation.

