**(c) Home-based Training.** Home-based training will increase gradually to reach the goal duration of 60 minutes allocated between strength training 3 days/week and aerobic, RMT and coordination training 5 days/week. Each session will begin with warm up before focused aerobic (pedal exerciser), strength, coordination, and RMT training, followed by cool down and stretching that matches the routines established during hospital-based training. Each patient will be given a portable, folding pedal exerciser that can be placed on the floor for leg pedaling or on a table for arm pedaling. Based on methods that successfully transition cardiac rehabilitation to the home, exercise physiologists will use weekly, remote, telephone-based/ VA Video Connect calls to maintain relationship, answer questions, adjust goals and coach patients regarding their personally tailored prehabilitation regimens. Patients will record details of each training session in log books, and they may return to the hospital biweekly to assess progress in physical performance, or their biweekly session may be completed via VA Video Connect, at which time exercise physiologists will (a) adjust training goals and exercises, (b) remediate technique as needed; and (c) assess the safety of continued home exercise. Family members or other caregivers can assist patients in completing the log books if needed. Training regimens such as these have been shown to be both safe and effective among the frail elderly.

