- Subjective Global Assessment of Nutrition (SGA) is the standard approach to nutritional assessment. It evaluates multiple domains of nutrition and reliably categorizes patients into 1 of 4 categories: normal, mild-, moderate- and severely malnourished. We will use the 7-point SGA (See Appendix) because it is sensitive to 1-point changes in as little as 1 month and has excellent inter-rater reliability ( $k=.726$ ).
- Compliance with Prehabilitation. Each patient will receive a prehabilitation log book in which they will record details about their home-based regimen, including the date of training, duration and intensity of exercise, IMT repetitions and threshold pressures, nutritional supplements consumed, dietary intake, and pedometer data (e.g., step counts at the beginning and end of each training session). They will be coached in the use of this log at each hospital session. Data from the logbook will be collected from patients weekly and entered into the database for analysis. In addition, because the pedometer stores 7 days of data, and the exercise physiologists will record daily step counts as a measure of overall activity at each hospital session.

- Barrier Assessment will be conducted through face-to-face or telephone interviews with participants who encounter difficulty with recruitment to, retention in, or adherence with the training regimens. Barriers, including advanced frailty and cognitive deterioration will be described and participants will be asked to propose facilitators that might remove or minimize the barrier in future. Interviews will not be elaborate, but the questions are detailed in the case report forms. No formal qualitative analysis will be conducted, but responses will be collated and summarized by research staff. We will not record responses or attempt to create verbatim transcripts, but instead, the research staff conducting the interviews will summarize patient responses and record those summaries in the case report forms.
- Health-Related Quality of Life will be measured with the Assessment of Quality of Life (AQoL-6D) that includes 20 items on a Guttman scale assessing 6 domains: independent living, mental health, relationships, senses, pain and coping. The utility score ranges from -.04 (state worse than death) to 1.0 (full health). It is sensitive to change with a minimum clinically important difference (MCID) of 0.06.

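### All-day step counts are read from a 7-day pedometer only at hospital sessions, so part of the home-phase record is lost, and more is lost for patients followed by video

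*Combined protocol and SAP*

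**What the plan says.** Under Compliance with Prehabilitation, C.5 describes two streams of pedometer data.

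- **Log book.** Patients enter the date, duration and intensity of training along with pedometer data. The example given is the step count at the start and end of a session. Log-book data are collected weekly.
- **Daily totals.** The reason and the rule are given together: "because the pedometer stores 7 days of data, and the exercise physiologists will record daily step counts", and they do so "as a measure of overall activity at each hospital session".

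The frequency of hospital contact depends on the phase.

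- **Hospital-based training, C.3(b):** "Twice weekly 1-hour hospital sessions will be closely monitored and continue until participants demonstrate" mastery and safe exertion.
- **Transition, C.3(a):** "we anticipate that many patients will safely transition to home-based exercise after 1-4 hospital-based sessions", although "safety concerns will require some patients to complete all exercise in monitored, hospital-based settings".
- **Home phase, C.3(c):** "they may return to the hospital biweekly to assess progress in physical performance, or their biweekly session may be completed via VA Video Connect". Separately, "exercise physiologists will use weekly, remote, telephone-based/ VA Video Connect calls" to support and coach patients.

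C.4 and Table 1 show that biweekly here means every two weeks. The remote assessment described in C.4 lists chair rises, short walks, breathing capacity and, where space allows, a modified 6-minute walk. It does not list a pedometer reading, and C.3(c) does not include one among the purposes of the weekly call.

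**The concern.** A 7-day memory gives a complete record only if it is read at least every 7 days. Twice-weekly hospital training meets that condition. A visit every 14 days does not, and a video session at which nobody reads the device recovers nothing. If the device overwrites its oldest day, as a 7-day store implies, the missed days cannot be recovered later.

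What is at stake is the only device-stored measure of overall activity that the plan describes for the home phase, which is the part of the programme whose feasibility is under test. The missingness would also be structured. Patients using the remote option would contribute the fewest days, so a summary of daily steps would mix different coverage by visit mode. For patients with only a surgery-day reading, it would rest on the last week before surgery alone.

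**Working it through.** The plan states no expected completeness for step counts, so there is no figure to reproduce. The check is a count of days.

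**Inputs from the documents**
- Memory: 7 days (C.5).
- Stated reading occasion: hospital sessions only (C.5).
- Home-phase visits: every 14 days, or remote (C.3(c), C.4, Table 1).
- Programme length: 3 to 6 weeks, with a 4-week limit for CABG and up to 6 weeks for non-cardiac thoracic patients (C.1, C.3).

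**Assumptions, not in the documents**
- A reading on day r recovers the seven completed days r−7 to r−1.
- In the main case the home phase starts on day 7, after one hospital week.
- Whether the day-of-surgery assessment counts as a hospital session is not stated, so both cases are shown.

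**Single interval.** Share lost = max(0, 1 − 7/interval). For 14 days: 1 − 7/14 = 50%. For 7 days or fewer: 0%.

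**4-week programme.** Home days are 7 to 27, which is 21 days.
- In person, readings on days 14 and 28: days 7–13 and 21–27 are recovered. Lost 7/21 = 33%.
- In person, no surgery-day reading: only days 7–13 are recovered. Lost 14/21 = 67%.
- All remote, surgery-day reading: days 21–27 are recovered. Lost 14/21 = 67%.
- All remote, no surgery-day reading: lost 21/21 = 100%.

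**6-week programme.** Home days are 7 to 41, which is 35 days.
- In person, readings on days 14, 28 and 42: 21 days are recovered. Lost 14/35 = 40%.
- In person, no surgery-day reading: 14 days are recovered. Lost 21/35 = 60%.
- All remote, surgery-day reading: 7 days are recovered. Lost 28/35 = 80%.
- All remote, no surgery-day reading: lost 35/35 = 100%.

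Counting the two-week visits from the transition on day 7 instead of from baseline gives the same totals in these cases.

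**Sensitivity to the transition point.** Transition was placed after 1, 2, 3 or 4 sessions, taken as days 0, 3, 7 and 10, with a surgery-day reading.

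| Programme | In person, every 14 days | All remote |
|---|---|---|
| 3 weeks | 0–50% lost | 36–67% lost |
| 4 weeks | 33–50% lost | 61–75% lost |
| 6 weeks | 40–50% lost | 78–83% lost |

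Without a surgery-day reading, in-person loss ranges from 50% to 100% across these scenarios, and all-remote loss is always 100%.

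**With weekly readings plus the day of surgery.** The interval never exceeds 7 days, and the loss is 0% in every scenario.

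**The case against.** Several points on the other side have force.

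- **The log book survives.** Date, duration, intensity and session step counts are collected weekly and do not depend on the device memory. A reader might infer that half or more of all home-phase activity data disappears. The documents do not support that. Only the stored all-day totals are at risk, and for in-person patients with a surgery-day reading the loss is at most half.
- **Steps are not shown to verify the logs.** A reader might take the pedometer to be the only check on self-report. C.5 calls the daily counts a measure of overall activity and gives them no verifying role. The prescribed aerobic work is seated leg or arm pedalling, and the rest is bands, transitional movements and breathing training. All-day steps could confirm little of this.
- **No planned analysis names daily steps.** C.8(b) estimates overall and exercise-specific adherence, and C.8(c) uses training duration and adherence for dose-response. Table 1 has no pedometer row. No stated estimate is shown to change.
- **Attendance may be more frequent.** In C.5, height and weight for BMI are taken weekly at the rehabilitation facility. Weekly attendance would remove the loss. But Table 1 schedules BMI every other week and C.3(c) makes the return visit optional, so this is a conflict to resolve and cannot be relied on to show that weekly readings will occur.
- **Silence is not prohibition.** The step-count example for the log book is only an example, the route of weekly log collection is not given, and the case report forms may say more. Staff might read the device remotely in practice. That is possible, but the only occasion C.5 gives for recording daily counts is the hospital session.

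These points limit the importance and scope of the problem. They do not close the gap between a 7-day store and a 14-day or remote schedule.

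**Conclusion.** The point holds, and it is minor. As written, the reading rule in C.5 does not fit the home-phase visit schedule. With one hospital week and a surgery-day reading, in-person patients lose about a third of home days in 4 weeks and two fifths in 6 weeks. All-remote patients lose about two thirds and four fifths, and all of them if the device is not read on the day of surgery. Patients who never leave hospital-based training lose nothing.

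These figures assume two-weekly visits kept on schedule, overwriting of days older than seven, and no unstated remote reading. The documents do not give the share of patients who would choose remote sessions, so no cohort-wide percentage can be stated.

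A reader might go further and conclude that the Aim 1 adherence estimates are compromised. That does not follow, because the weekly log-book data are unaffected by this mechanism. The damage is to a supplementary compliance and activity measure, whose coverage would differ between remote and in-person patients.

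**What to change.** In C.5, where daily counts are now recorded only at hospital sessions, state that they are recorded at each weekly telephone or VA Video Connect call, at each hospital session and on the day of surgery. On calls, the patient or caregiver reads out the seven stored daily totals, and the form records whether each reading came from staff or from the patient. Separately, reconcile the weekly BMI attendance in C.5 with the every-other-week schedule in C.4 and Table 1.

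The cost is a minute or two on a call that already takes place and a short addition to the case report form. No visit is added. There are two limitations. Counts taken by phone or video are patient-reported from the device, which is why the source should be recorded. And a call that slips beyond seven days still loses one day for each day of delay.

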#### Research Procedures/Interventions:

**C.1. Overview.** In this single-arm pilot study, we will enroll a consecutive cohort of up to 50 Veterans identified as frail using a standardized frailty assessment and scheduled for major cardiothoracic surgery at the VA Pittsburgh Healthcare System. The 3-6 week long prehabilitation regimen will include: (a) aerobic conditioning, (b) strength and coordination training, (c) respiratory muscle training, and (d) nutritional coaching and supplementation. Pre- and post-prehabilitation assessments will include: (a) frailty; (b) physical function; (c) pulmonary function; (d) nutrition; and (e) health-related quality of life. Using physical performance tests, biomarkers, chart review, survey instruments, and patient logs, we will assess the feasibility of the recruitment, randomization, retention and assessment procedures, compensating patients for their time. Prehabilitation will not last more than 4 weeks for CABG patients. However, for non-cardiac thoracic patients, prehabilitation may be extended out to 6 weeks if the surgeon and patient so choose.

**C.2. Eligibility criteria.** We will recruit frail patients (i.e., RAI $\geq$ 16 and Physician /Provider request for patient with RAI<16) scheduled for a CABG or Valve Surgery. Major non-cardiac thoracic surgery is defined according to VA Surgical Quality Improvement Program (VASQIP) criteria that include cases requiring general, epidural, or spinal anesthesia. It includes 193 unique CPT codes ranked by complexity (26 standard, 146 intermediate, and 21 complex) and excludes 58 low risk “minor” surgical procedures with limited morbidity (e.g., bronchoscopy, percutaneous lung biopsy). From these major surgeries, we will include those procedures that deliberately violate the visceral or parietal pleura with something larger than an 18 gauge needle. For example, we will include lung and esophagus resections of all kinds, but exclude thoracentesis. Exclusion criteria are designed to ensure participant safety in prehabilitation exercises (e.g., low-risk, stable cardiac disease without significant symptoms, arrhythmias, hemodynamic instability or critical coronary lesions). Based on historical data, we expect 2/3rds of eligible

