**(c) Ascertain the feasibility of measuring changes over time in frailty, physical function, pulmonary function, nutrition, and health-related quality of life at baseline, the day of surgery, and 30 and 90 days after surgery [Aim 2].** We will summarize the time required to complete each assessment as well as the completeness of data, estimating completion rates with CIs. Graphical analyses will assess simple changes in frailty, physical performance, pulmonary function, nutrition and quality of life over the study period. Although sample size will limit model fit, we will prepare analyses for the larger trial by developing simple mixed models to explore changes over time (baseline and every other week up to the day of surgery, and then 30 and 90 days after). Separate models for each outcome will assess changes, including a fixed effect for time and a random effect for subject. The type of mixed model will depend on the outcome variable with linear mixed models for continuous variables (e.g., RAI, SPPB, 6MWT, MIP, MEP, etc) and generalized mixed models for ordinal/categorical variables (e.g., SGA, frailty phenotype). We will also explore dose-response relationships based on the actual duration of and adherence to the training regimen.

**(d) Explore changes in postoperative mortality, major complications, length of hospital stay, and level of independent living using case-matched historical controls [Exploratory Aim].** We will match each participant to an historical control using local VASQIP data. VASQIP data include variables sufficient to calculate the RAI as well as details about the patient's procedure, comorbidities, outcomes, and a highly reliable prediction of postoperative 30-day mortality. Each historical control will be chosen from VAPHS VASQIP data from the 2 years prior to the study start and matched to the enrolled participant based on procedure, age, RAI score, and VASQIP predicted mortality. We will summarize separately the total number of deaths and major complications at 30 and 90 days for all patients, estimating proportions with associated CIs for the intervention and historical control groups. We will also compute summary statistics (mean, median, standard deviation, range) for length of hospital stay and return to independent living. We will then attempt to assess if differences exist between the groups with regard to these post-operative measures.

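### Historical controls are not limited to scheduled cases or screened by the participants' exercise-safety exclusions, and complications are summarised at 90 days but scheduled only at 30

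*Combined protocol and SAP*

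**What the plan says.** **Controls.** C.8(d) states: "We will match each participant to an historical control using local VASQIP data". Controls come from the two years before study start and are "matched to the enrolled participant based on procedure, age, RAI score, and VASQIP predicted mortality". The section describes the VASQIP risk score as "a highly reliable prediction of postoperative 30-day mortality". It then summarises deaths, major complications, length of stay and return to independent living, and adds: "We will then attempt to assess if differences exist between the groups". No test, significance level or decision rule is named.

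**Participants.** C.1 enrols frail Veterans "scheduled for major cardiothoracic surgery at the VA Pittsburgh Healthcare System". C.2 says: "Exclusion criteria are designed to ensure participant safety in prehabilitation exercises". The only content given is an example: "low-risk, stable cardiac disease without significant symptoms, arrhythmias, hemodynamic instability or critical coronary lesions". C.3(a) adds that staff will start withdrawal of patients who prove unable, cognitively or physically, to do the exercises safely.

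**Timing of complications.** C.8(d) summarises the "total number of deaths and major complications at 30 and 90 days for all patients". Table 1 labels the major-complications row as a 30-day item and marks it only in the 30-day column; mortality is marked at both 30 and 90 days. C.5 refers to VASQIP coding rules in an appendix, states no time window, and authorises the nurse abstractor to code participating patients. C.4 plans chart review of major complications, also without a stated window.

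**The concern.** Entry criteria that remove unscheduled and unstable patients operate on one side of the comparison only. Under the plan as written, an unscheduled case, or one with hemodynamic instability, could be matched to a participant if procedure, age, RAI and predicted mortality are close enough. If such patients do worse after surgery than the matching variables predict, the control group looks worse for reasons unrelated to prehabilitation. Section 2.0 says the findings will inform the design of a larger randomised trial, so the comparison should be between like patients even if it carries little weight.

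The timing conflict is a separate matter. A 90-day complication comparison needs the same ascertainment in both groups, and the documents do not set that out.

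**Working it through.** The documents give no figure for this comparison to reproduce: the sample of up to 50 has no stated statistical basis. The check is mainly one of text.

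**Step 1. Selection, side by side.**

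| Condition | Participants | Historical controls |
|---|---|---|
| Scheduled operation | Required (C.1, C.2) | Not stated |
| Exercise-safety exclusions | Applied (C.2) | Not stated |
| Withdrawal for insufficient capacity | Possible (C.3(a)) | No counterpart |
| Procedure, age, RAI, predicted mortality | Define the match | Matched (C.8(d)) |

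**Step 2. Does matching stand in for the missing criteria?** It may do so in part. The inputs to the VASQIP prediction are not listed, so the documents do not show that it captures urgency or cardiac instability. It is described as a prediction of 30-day mortality, while the comparison also covers complications, length of stay and independent living.

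**Step 3. Can the shift be sized?** Suppose there is no true effect and no reduction by matching. Let patients who meet the entry criteria have complication risk p. Let a share f of controls be patients who would have been excluded, with risk k times p.

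- Control risk = p(1 − f) + f·k·p
- Apparent benefit = f·p·(k − 1)

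The documents give none of p, f or k. Purely as an illustration, with assumed k = 2 and f from 10% to 40%:

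- p = 10%: from 0.1 × 0.10 × 1 = 1 point to 0.4 × 0.10 × 1 = 4 points.
- p = 20%: from 0.1 × 0.20 × 1 = 2 points to 0.4 × 0.20 × 1 = 8 points.

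Matching would lower these by an amount that cannot be calculated. They are not estimates for this trial.

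**Step 4. Could the results reveal a shift of that order?** At the maximum of 50 pairs, ignoring pairing and taking equal risk in both groups, the 95% half-width for a risk difference is 196 × √(2p(1 − p)/50) points.

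- p = 10%: 196 × √0.0036 = 11.8 points.
- p = 20%: 196 × √0.0064 = 15.7 points.

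These figures describe sampling precision only and would be the same with perfectly eligible controls. They show that a shift of a few points could not be recognised afterwards, which is why it is better handled when controls are chosen.

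**Step 5. Complication time points.** C.8(d) gives 30 and 90 days; Table 1 gives 30 days. C.4 leaves room for later chart review in participants. No section names a source of 90-day complications in controls.

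**The case against.** **The aim is exploratory and matching handles risk.** C.8 says analysis will focus on feasibility, and controls are matched on frailty, age, procedure and predicted mortality. This stands as a reason for low severity and as a reason to expect some reduction in bias. It does not replace applying the same entry criteria to both groups.

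**The direction is inferred.** This also stands. C.2 admits patients with RAI below 16 at a provider's request; if those patients are sicker than their score suggests, matching on RAI could push the other way. A reader might infer that the plan will show a false benefit of some known size. The documents do not support that: they give no input for the size, and the sampling half-widths do not measure it.

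**Complications at 90 days.** A reader might infer that this comparison has no planned data at all. That goes too far, because the chart review in C.4 has no stated window and the coding appendix is not in the public text. One could also read the two time points in C.8(d) as belonging to deaths only, although the sentence joins deaths and complications. What remains is a conflict with Table 1 and an unnamed control source.

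**The exclusions may be listed elsewhere.** They appear here only as an example, and a full list may exist outside the public text. That would make the screening easier; it would not extend the exclusions to controls.

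**Unpaired analysis.** A reader might infer that the plan ignores the matching when it compares groups. C.8(d) does not specify an unpaired method, so this is not a defect of the plan.

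**Conclusion.** The point holds as a minor one, in two parts. First, participants are selected by scheduled status and exercise-safety exclusions, and no section applies either to the controls. A bias favouring prehabilitation is plausible but not demonstrated, and its size is unknown; the figures in the working rest on assumed risks and shares. Second, C.8(d) and Table 1 disagree on when major complications are assessed, and no source of 90-day complications in controls is given.

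The severity is limited because the aim is exploratory, carries no decision rule, and is not said to set an effect size for the later trial. The conclusion assumes that no part of the plan outside the public text already sets eligibility for the control pool.

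**What to change.** 1. Before matching, restrict the VASQIP pool to scheduled cases and remove cases that the participants' exclusions would have ruled out, as far as VASQIP or chart data allow. This needs the exclusions as an explicit list. Report the number of cases removed and the number of participants left unmatched.
2. State as limitations any criterion that cannot be applied to past records, and that withdrawal for insufficient capacity under C.3(a) has no counterpart in controls. Keep withdrawn participants who go on to surgery in the comparison where outcome data exist.
3. Reconcile C.8(d) with Table 1: either limit the complication comparison to 30 days, or abstract complications to 90 days in the same way in both groups.
4. Optional: report the between-group difference with a matched-pair confidence interval. In complete pairs this leaves the point estimate unchanged and may give a modest gain in precision.

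The cost is some record screening at the same site, a smaller control pool and possibly a few unmatched participants. Item 3 is a wording change unless 90-day abstraction is chosen; that would add chart work in both groups, and for controls the coding authorisation in C.5, which covers participating patients, would have to be extended.
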